**Table 1 List of Abbreviations and Definitions of Terms**

ADR	Adverse Drug Reaction
AE	Adverse Event
AESI	Adverse Event of Special Interest
CCI	CCI
BCDVA	Best Corrected Distance Visual Acuity
BLA	Biologics License Application
CFR	Code of Federal Regulations
CRA	Clinical Research Associate
CRF	Case Report Form
CRO	Contract Research Organization
DHHS	Department of Health and Human Services
DSUR	Development Safety Update Report
eCRF	Electronic Case Report Form
EDC	Electronic Data Capture
ETDRS	Early Treatment Diabetic Retinopathy Study
FAS	Full Analysis Set
FDA	Food and Drug Administration
GCP	Good Clinical Practice
GPS2	Global Pharmacovigilance, Safety and Surveillance
HIPAA	Health Insurance Portability and Accountability Act
ICF	Informed Consent Form
ICH	International Conference on Harmonization
IDEEL	Impact of Dry Eye on Everyday Life
IEC	Independent Ethics Committee
IND	Investigational New Drug
IRB	Institutional Review Board
LNGFR	Low-Affinity Nerve Growth Factor Receptor
Log MAR	Logarithm of the Minimum Angle of Resolution
mcg/mL	Microgram per milliliter
mNGF	Murine Nerve Growth Factor
MOP	Manual of Procedures
NGF	Nerve Growth Factor
CCI	

CCI

NK	Neurotrophic Keratitis/Keratopathy
CCI	
P75NTR	P75 Neurotrophin Receptor
PED	Persistent Epithelial Defect
PID	Patient Identification
PI	Principal Investigator
rhNGF	Recombinant Human Nerve Growth Factor
SAE	Serious Adverse Event
SAP	Statistical Analysis Plan
SLE	Slit-Lamp Examination
SUSAR	Suspected Unexpected Serious Adverse Reaction
TFBUT	Tear Film Break Up Time
TrkA	Tropomyosin Receptor Kinase A

1 STUDY SYNOPSIS

CLINICAL STUDY SYNOPSIS:	
Study Number	NGF0122
Title of Study	A long-term extension study to evaluate the safety and efficacy of OXERVATE™ 0.002% (20 mcg/mL) cenegegermin-bk bj ophthalmic solution in patients with Stage 1 Neurotrophic Keratitis who were enrolled in the DEFENDO Study
Short Title	DEFENDO Long-Term Follow-up Study
EudraCT N°/IND	115892
Study Centers (Country)	4 US Study Centers
Development Phase	IV
Study Objectives	
Primary Objective
 
The primary objectives are to evaluate the long-term safety and efficacy (healing) of OXERVATE™ 0.002% (20 mcg/mL) cenegegermin-bk bj ophthalmic solution in Stage 1 Neurotrophic Keratitis (NK) patients who enrolled in the DEFENDO Study.
 
Secondary Objective
 
The secondary objectives are to evaluate the long-term efficacy of OXERVATE™ 0.002% (20 mcg/mL) cenegegermin-bk bj ophthalmic solution in terms of Corneal Sensitivity, Schirmer I Test, Tear Film Break Up Time (TFBUT), Best Corrected Distance Visual Acuity (BCDVA), and Quality of Life at 24 and 30 months.

	
CC1 [REDACTED]

Design and Methodology	
This clinical study will be a multi-center, open label, long-term follow-up study of the patients who were enrolled in the DEFENDO Study who had Stage 1 Neurotrophic Keratitis (NK) who were treated with OXERVATE™ 0.002% (20 mcg/mL) cenergermin-bk bj ophthalmic solution.
 
The DEFENDO Long-Term Follow-up Study will have follow-up with the patients at month 24 and 30 post-treatment in the DEFENDO Study: All patients will be evaluated in a real-world setting post the enrollment in the DEFENDO Study through 30 months. Patients will be treated per standard of care as determined by the Investigator CC [REDACTED]
 
The original DEFENDO Study duration was for a total of 34 weeks: a screening period of 2 weeks, followed by enrollment in 8 weeks of OXERVATE™ treatment and an Off-Treatment Follow-Up of 6 months.
 
 • After completing enrollment in the original DEFENDO Study, patients will be invited to enter the DEFENDO Long-Term Follow-up Study (all standard of care is permitted). Two (2) additional long-term follow-up visits will occur at 24- and 30-months to evaluate long-term clinical outcomes.

	
All patients enrolled in the DEFENDO Study who are not meeting exclusion criteria and/or are not lost to follow-up will be eligible for the DEFENDO Long-Term Follow-up Study.
 
During the DEFENDO Long-Term Follow-up Study, the patients may be treated at the physician's discretion. Any concomitant treatment must be documented. If warranted for patient safety, the Investigator may elect to see the patient at an Unscheduled Visit(s) to evaluate the patient.

Number of Patients	Up to 37
Main Criteria for Inclusion/Exclusion	
Inclusion Criteria - To be eligible for inclusion into this study, each patient must fulfil the following inclusion criteria:
 
 1. Previously enrolled in the DEFENDO Study. 2. Satisfy all Informed Consent requirements. 
 • The patient and/or his/her legal representative has read, signed, and dated the IRB approved Informed Consent document before any study-related procedures are performed. 3. Must have the ability and willingness to comply with study procedures. 
Exclusion Criteria - Patients who meet any of the following criteria are NOT eligible for inclusion in the study:
 
 1. Participating in another study that involves treating the study eye. 
 a. Participation in non-ocular studies is acceptable provided that the treatment is not considered to be confounding with the DEFENDO Long-Term Follow-up Study, in the opinion of the Investigator.
Duration of Treatment	No study treatment will be provided
Reference product, Dosage and Mode of Administration	N/A

Efficacy Endpoints	
 • Percentage of patients who have corneal epithelial healing at 24 months and 30 months of the long-term follow-up. 
 ◦ Percentage of patients who had corneal epithelial healing at week-8 in the DEFENDO Study, who maintain healing at month 24 and month 30 of the long-term follow-up. ◦ Percentage of patients who did not have corneal epithelial healing at week-8 in the DEFENDO Study who have a healed corneal epithelium at month 24 and month 30 of the long-term follow-up. • Percentage of patients who achieved an improvement in corneal sensitivity at 24 months and 30 months of the long-term follow-up. 
 ◦ Percentage of patients who achieved an improvement in corneal sensitivity at week-8 in the DEFENDO Study who still have improvement in corneal sensitivity at 24 months and 30 months of the long-term follow-up. ◦ Percentage of patients who did not achieve an improvement in corneal sensitivity in the DEFENDO Study who have improvement in corneal sensitivity at 24 months and 30 months of the long-term follow-up. • Change from the Baseline Visit in the DEFENDO Study in Schirmer I scores at 24 months and 30 months of the long-term follow-up. • Change from the Baseline Visit in the DEFENDO Study in TFBUT at 24 months and 30 months of the long-term follow-up. • Change from the Baseline Visit in the DEFENDO Study in BCDVA at 24 months and 30 months of the long-term follow-up.
---------------------------	-------------------------------------------------------------------------------------------------------------------------------------------------------------------------------------------------------------------------------------------------------------------------------------------------------------------------------------------------------------------------------------------------------------------------------------------------------------------------------------------------------------------------------------------------------------------------------------------------------------------------------------------------------------------------------------------------------------------------------------------------------------------------------------------------------------------------------------------------------------------------------------------------------------------------------------------------------------------------------------------------------------------------------------------------------------------------------------------------------------------------------------------------------------------------------------------------------------------------------------------------------------------------------------------------------------------------------------------------------------------------------------------------------------------------------------------------------------------------------------------------------------------------------------------------------------------------------------------------------------------------------------------------------------------------------

Statistical Methods	
The sample size for this study is not based on hypothesis-testing and power considerations but is determined by the number of patients from the DEFENDO Study who will rollover to the DEFENDO Long-Term Follow-up Study. The DEFENDO Study enrolled a total of 37 patients.
 
The Full Analysis Set (FAS) will consist of all patients who are enrolled (with signed and dated IC) in the DEFENDO Long-Term Follow-up Study. The FAS population will be used for the presenting efficacy and safety results.
 
Appropriate descriptive statistics will be produced according to the nature of the variable. For continuous data, number of observations, mean, standard deviation, median, range (minimum and maximum) and 95% confidence intervals will be presented. For categorical data, frequency distributions and percentages with exact 95% confidence intervals will be presented.
 
Baseline demographic and background variables will be summarized based upon the data originally collected in the DEFENDO Study. The number of patients who enroll in the DEFENDO Long-Term Follow-up Study and the number and percentage of patients who reach 24 months and 30 months of the long-term follow-up will be presented along with the frequency and percentage of patients who withdraw.
 
Efficacy endpoints will be analyzed at each available time point by appropriate inferential tests versus baseline and/or week 8. All tests will be descriptive in nature, no formal hypothesis test will be conducted.
 
Adverse events (AEs) will be coded by preferred term and system organ class using the latest version of the Medical Dictionary for Regulatory Activities and will be summarized overall.

----------------------------	----------------------------------------------------------------------------------------------------------------------------------------------------------------------------------------------------------------------------------------------------------------------------------------------------------------------------------------------------------------------------------------------------------------------------------------------------------------------------------------------------------------------------------------------------------------------------------------------------------------------------------------------------------------------------------------------------------------------------------------------------------------------------------------------------------------------------------------------------------------------------------------------------------------------------------------------------------------------------------------------------------------------------------------------------------------------------------------------------------------------------------------------------------------------------------------------------------------------------------------------------------------------------------------------------------------------------------------------------------------------------------------------------------------------------------------------------------------------------------------------------------------------------------------------------------------------------------------------------------------------------------------------------------------------------------------------------------------------------------------------------------

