7.1 STUDY VISITS AND EXAMINATIONS AND TREATMENT VISITS

7.1.1 Visit 1: 24-Month Long-Term Follow-Up

The 24-month long-term follow up is considered from the completion of 8-weeks of treatment. Site staff will conduct the following assessments in the order outlined below:

1. **Inclusion/Exclusion Criteria:** Inclusion/Exclusion criteria will be reviewed, and study eligibility will be determined.
2. **Informed Consent/Health Insurance Portability and Accountability Act (HIPAA):** Explain the purpose and nature of the study and have the patient or legally authorized representative read, sign, and date the IRB approved Informed Consent Form (ICF). Provide a photocopy of the signed document to the patient and place the original signed document in the patient's chart.
3. **Demographics, Medical and Ocular History:** These data from the DEFENDO Study will be carried forward into the current study's electronic data capture (EDC) System; thus, they do not need to be captured separately for this study.
4. **Record AE:** Record any AE since completing the DEFENDO Study in the AE eCRF. Data for AEs that have occurred since the completion of the DEFENDO Study should be obtained from retrospective chart review and / or patient interview. Additional information may be requested via medical records from all applicable healthcare providers, if necessary.
5. **Concomitant and Prior Ocular and Systemic Medications:** Record any concurrent ocular or non-ocular medications including information on all concomitant and previous medications used since completing the DEFENDO Study in the Concomitant Medications eCRF ([Section 6.2](#)). Data for topical ocular medications taken since the patient completed the DEFENDO Study should be obtained from retrospective chart review and / or patient interview. Additional information may be requested via medical records from all applicable healthcare providers, if necessary.

6. **IDEEL (Impact of Dry Eye on Everyday Life):** This questionnaire will be assessed by the patient using a self-administered format. This questionnaire is designed to assess health-related quality of life in patients with visual impairments by representing the patient perspective on the impact of vision problems on functioning.

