In line with CT3 Detailed Guidance and International Conference on Harmonization (ICH) E2A provisions, although the Investigator does not usually need to actively monitor patients for AEs once the study has ended, if the Investigator becomes aware of a SAE occurring to a patient after that patient has ended his/her participation in the study – including the long-term follow-up (whether study completion or withdrawal), the SAE should be reported by the Investigator to the Dompé PPD Pharmacovigilance. Such “post-study cases” should be regarded for expedited reporting purposes as though they were study reports. Therefore, a causality assessment and determination of expectedness are needed for a decision on whether expedited reporting is required.

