10.1 SAMPLE SIZE

The sample size for this study is not based on hypothesis-testing and power considerations but is determined by the number of patients from the DEFENDO Study who will rollover to the DEFENDO Long-Term Follow-up Study. The DEFENDO Study enrolled a total of 37 patients.

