10.3 STATISTICAL METHODOLOGY

Statistical analysis will be performed by the clinical research organization (CRO) appointed by Dompé.

Appropriate descriptive statistics will be produced by treatment arms according to the nature of the variable. For continuous data, number of observations, mean, standard deviation, median and range (minimum and maximum) and 95% confidence intervals will be presented. For categorical data, frequency distributions and percentages with exact 95% confidence intervals will be presented.

Unless otherwise specified, the significance level used for statistical testing (for descriptive purposes) will be 0.05 and two-sided tests will be used. All patient data collected on the CRF will be listed by patient and center.

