1.1 Study Objectives

Primary Objective

The primary objectives are to evaluate the long-term safety and efficacy (corneal epithelial healing) of OXERVATE™ 0.002% (20 mcg/mL) cenegermin-bk bj ophthalmic solution in Stage 1 Neurotrophic Keratitis (NK) patients who enrolled in the DEFENDO Study.

Secondary Objective

The secondary objectives are to evaluate the long-term efficacy of OXERVATE™ 0.002% (20 mcg/mL) cenegermin-bk bj ophthalmic solution in terms of Corneal Sensitivity, Schirmer I Test, Tear Film Break Up Time (TFBUT), Best Corrected Distance Visual Acuity (BCDVA), and Quality of Life at 24 and 30 months.

CCI

CCI

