6.1 Adverse Events

Adverse events will be classified according to the MedDRA to the levels of SOC and PT. SOC will be sorted alphabetically and PT within each SOC will be sorted by overall descending order of frequency. All events in the clinical database regardless of when they occurred will be provided in data listings.

The number and percentage of subjects experiencing one or more events will be tabulated by SOC and PT. In addition, similar tables by SOC and PT will be displayed further by maximum severity, and by closest relationship to treatment. For summary, the AEs with relationship to treatment reported as "None" or

“Unlikely” are considered “Not Related”, and “Possible”, “Probable”, or “Highly Probable” are considered “Related”.

Summary tables will be prepared also for the number and percentage of subjects experiencing one or more events during the entire extended follow-up period.

In summary tables for ocular adverse events, AEs occurring in both eyes will be summarized once at the greater severity or closer relationship to study drug.

A listing of serious AEs (SAEs) will be also provided.

A glossary listing that shows the verbatim terms assigned to each SOC and PT will be provided.

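### The AE tables reach back to the end of DEFENDO but count only patients who attended Month 24 or Month 30, so an earlier death cannot appear in them

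*Protocol*

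**What the plan says.** **Target population.** SAP 1.1 sets the primary objective as long-term safety and efficacy in "Stage 1 Neurotrophic Keratitis (NK) patients who enrolled in the DEFENDO Study". Protocol 10.1 gives the size of that cohort: "The DEFENDO Study enrolled a total of 37 patients".

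**Who is counted.** The protocol (Synopsis and 10.2) defines the FAS by signed consent: "The Full Analysis Set (FAS) will consist of all patients who are enrolled (with signed and dated IC) in the DEFENDO Long-Term Follow-up Study". SAP 1 says the SAP supersedes the protocol's statistical considerations, and SAP 2.5 adds the condition of attending Month 24 and/or Month 30. SAP 6 bases every safety summary on that set. SAP 2 limits the data listings to enrolled subjects, and SAP 3 and 3.1 place disposition on the FAS.

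**When patients enter.** Table 2 of the protocol marks consent at Visit 1, at 24-27 months. Sections 7.1.1 and 7.1.2 count the visits from the end of the 8-week treatment. Section 4.3 ends DEFENDO follow-up 6 months after treatment.

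**What period is covered.** Protocol 7.1.1 instructs sites: "Record any AE since completing the DEFENDO Study in the AE eCRF", using chart review and/or interview. SAP 1.3.4.1 has the same starting point. SAP 6.1 adds: "Summary tables will be prepared also for the number and percentage of subjects experiencing one or more events during the entire extended follow-up period". The AE table titles in SAP Appendix 2 name the same period.

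**The concern.** The population in the objective and the population in the tables differ in a way that matters for safety. To be counted, a patient must be alive and attend a visit 24 months or more after treatment, yet the event window opens about 18 months before the first such visit. For that part of the window a zero count of deaths is fixed by the rules for entering the table and carries no information.

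A report of no deaths during extended follow-up, or a low SAE percentage, could then be read as evidence of long-term safety. Nothing planned would correct that reading. Protocol 10.3.1 reports how many enrol, reach each visit and withdraw, but not why others never entered or whether they were alive. Three patients discontinued DEFENDO because of adverse events (Protocol 3.2). Inclusion criterion 1 would admit them, but no planned output shows whether they entered.

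**Working it through.** **1. A planned figure to reproduce.** There is none. Protocol 10.1 says: "The sample size for this study is not based on hypothesis-testing and power considerations". The 37 is a head count, so the check uses the documents' own timing.

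**2. Inputs.** Months are counted from the end of treatment.
- DEFENDO completion: Month 6 (Protocol 4.3).
- Visit 1 (V1): Months 24-27. Visit 2 (V2): Months 30-33 (Protocol Table 2).
- SAP 2.2 labels: end of DEFENDO follow-up Week 32, Month 24 = Week 96, Month 30 = Week 120.
- Assumption: extended follow-up starts at DEFENDO completion. SAP 1.3.2 and 1.3.4.1 support this, but the SAP does not define it.

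**3. Share of the window before Visit 1** = (V1 - 6) / (V2 - 6).

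| V1 | V2 | Before V1 (months) | Whole window (months) | Share |
|---|---|---|---|---|
| 24 | 30 | 18 | 24 | 75.0% |
| 24 | 33 | 18 | 27 | 66.7% |
| 27 | 33 | 21 | 27 | 77.8% |
| 27 | 30 | 21 | 24 | 87.5% |

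On the SAP week labels the share is (96 - 32) / (120 - 32) = 64/88 = 72.7%.

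**4. Which deaths can be counted.** A death enters an FAS table only if the patient first attended Month 24 or Month 30. A death before the first attended visit therefore has probability zero of being tabulated, whatever the true rate. SAP 2.5 also admits patients with only a Month 30 visit. For them the unobservable stretch is 30 - 6 = 24 months, up to 33 - 6 = 27, which is the whole window.

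**5. Sensitivity to the start date.** SAP 2.2 uses the term extended follow-up only as a label for the two late visits. If the period began at Month 24, the table window would be 30 - 24 = 6 months, the share in step 3 would not apply, and events from the look-back would appear only in the listings. Protocol 9.3 instead starts AE recording at DEFENDO consent, which would lengthen the window. The three starting points do not agree.

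**6. Illustration only.** The documents give no count of deaths or non-entrants. Assume d deaths before Visit 1, every survivor enrols, and no later deaths. The intervals are exact two-sided 95% (Clopper-Pearson); for 0/n the upper limit is 1 - 0.025^(1/n).

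| d (assumed) | FAS table | All 37 |
|---|---|---|
| 0 | 0/37 (0-9.5%) | 0/37 (0-9.5%) |
| 1 | 0/36 (0-9.7%) | 1/37 = 2.7% (0.1-14.2%) |
| 2 | 0/35 (0-10.0%) | 2/37 = 5.4% (0.7-18.2%) |
| 3 | 0/34 (0-10.3%) | 3/37 = 8.1% (1.7-21.9%) |
| 4 | 0/33 (0-10.6%) | 4/37 = 10.8% (3.0-25.4%) |

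With an assumed annual mortality m, p = 1 - (1 - m)^1.5 over 18 months, and the chance of at least one death among 37 is 1 - (1 - p)^37. For m = 1%, 2% and 5% this is 43%, 67% and 94%, with 0.55, 1.1 and 2.7 deaths expected. These rates are assumptions and do not come from the documents.

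**The case against.** **No bias is demonstrated.** This stands. Without a count of deaths or non-entrants, a reader might infer that the safety result is survivor-biased as a matter of fact. The documents show only that the design cannot register such deaths.

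**Consent only at the 24-month visit is too absolute.** This also stands. Protocol 5.1 requires consent before study procedures and sets no month, and SAP 2.5 admits patients seen only at Month 30. The point does not depend on the consent date: the attendance condition in SAP 2.5 would exclude even a patient who consented early and died before a visit.

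**Disabling illness is not excluded by construction.** This stands too. A legal representative may sign (Protocol 5.1 and 7.1.1), so a seriously ill patient who can be brought to a visit may enter. Exclusion is certain for death and only likely for illness that prevents attendance or compliance.

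**Selection and look-back are disclosed.** In part. Protocol 5 says entrants are those not lost to follow-up, 7.1.1 says earlier events are collected retrospectively, and the number enrolled can be set against 37. Table 14.1.1 has no stated FAS restriction and might show the count. None of this gives reasons for non-entry or vital status.

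**Known deaths still reach the sponsor.** In part. Under Protocol 9.4.1, SAEs that an investigator learns of after a patient's participation "should be regarded for expedited reporting purposes as though they were study reports". A reader might infer that such deaths go wholly uncaptured, and the documents do not support that. But the route is passive, it is unclear whether it covers DEFENDO patients who never entered this study, and nothing brings those reports into the study tables.

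**The study is exploratory and single-arm.** True (SAP 2.9), but beside the point. The issue is who can be counted, and no hypothesis test is involved.

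**Conclusion.** The point holds in this form: the planned AE and death percentages describe patients who survived to Month 24 or Month 30 and attended, while the primary safety objective concerns all 37 who enrolled in DEFENDO. If extended follow-up starts at DEFENDO completion, about three quarters of the nominal window (67-88% over the visit windows) could not have produced a tabulated death. That share rests on a start date the SAP leaves undefined.

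The conclusion concerns what the tables are able to show. It does not establish that any death was missed. The size of any bias is unknown and may be nil. The change is still worth making, because a zero fixed by design would otherwise be presented without a warning under a primary objective.

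**What to change.** 1. **SAP 3.1 and 6.1:** add one accounting table of all 37 DEFENDO patients: entered; not entered because of death, illness, refusal or loss to follow-up; status unknown. Use only information that the sponsor or sites already hold, or that is reported under Protocol 9.4.1, within consent and privacy rules. Non-entrants did not sign this study's consent or HIPAA form.
2. **Deaths:** report known deaths after DEFENDO exit over 37, labelled as a minimum, with the number of unknown status beside it.
3. **Period:** define the start of extended follow-up in SAP 2.2, and reconcile it with SAP 1.3.2 and 1.3.4.1 and with Protocol 9.3.
4. **Footnote** to Tables 14.3.1.1-14.3.1.4 and Listing 14.3.2: *Results are conditional on attending the Month 24 and/or Month 30 visit. Deaths before the first attended visit could not be observed in this analysis set.*

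**Cost.** SAP wording, one extra table, and a reconciliation of the DEFENDO patient list with the safety database. No new visits and no change to endpoints. Some patients will remain of unknown status and must be shown as such. If the SAP is not reopened, Protocol 10.3.5 allows the addition to be made and documented in the study report.
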